Official Title of the study:

A-HACK Study: Addressing Heavy Alcohol use Consumption with Kudzu

NCT number:

NCT03709043

Document Type:

Study Protocol and Statistical Analysis Plan

Date of the document:

03/12/2021

CLINICAL PROTOCOL

1.1 Overview and rationale for a pilot placebo-controlled trial and kudzu.

We propose to conduct a 12-week pilot with 1- and 3-month post-treatment follow-up, double-blind, placebo-controlled study of targeted kudzu extract among binge-drinkers with AUD at high risk for acquiring or transmitting HIV and other sexually transmitted infections (STIs). This intervention could benefit this population in two ways: reductions in binge drinking may limit harms associated with alcohol use and decrease alcohol-related sexual risk behaviors. This study will determine whether targeted oral kudzu extract (2 grams), taken on an as-needed basis, is an efficacious, tolerable and acceptable strategy among binge-drinkers who are at high risk for acquiring or transmitting HIV and other STIs. If kudzu extract is shown to be a viable strategy among binge-drinking individuals, it may ultimately expand the available interventions for this populations to reduce their alcohol consumption.

1.2 Specific Aims

The primary objectives of this study are as follows:

1. To determine the efficacy of targeted kudzu versus placebo in reducing binge drinking, as determined by number of binge drinking days in timeline follow-back (TLFB), by treatment arm.
2. To determine the efficacy of targeted kudzu versus placebo in reducing recent alcohol consumption, as determined by the proportion of ethyl glucuronide (EtG) positive urines, by treatment arm.
3. To determine the efficacy of targeted kudzu versus placebo in reducing alcohol-associated sexual risk behaviors and incidence of STIs, as determined by audio computer assisted survey instrument (ACASI) data and STI (syphilis, *Neisseria gonorrhoea*, *Chlamydia trachomatis* testing, HIV) testing, by treatment arm.
4. To evaluate the tolerability and acceptability of targeted kudzu versus placebo, as determined by adverse clinical event rates and medication adherence (via data from MEMs cap dispenser monitoring and self-report from SMS texts and TLFB), by treatment arm.

1.3 Facilities and Investigator.

Study activities will take place at the Center on Substance Use and Health (CSUH) of the San Francisco Department of Public Health (SFDPH), a well-established clinical trial site. [name] has a joint appointment as a Senior Research Scientist at SFDPH. He has conducted research at this field site since 2008. The site is centrally located near multiple transit lines with convenient access for residents of multiple neighborhoods with high rates of alcohol use. We have had remarkable success recruiting and retaining alcohol and substance users at this location. Study staff have access to both **SFDPH** and **University of California, San Francisco**. The paired effort of these institutions has proven highly effective in both research and clinical care in San Francisco.

1.3.a. Form 1572

See Appendix B

1.3.b. Sponsor-Investigator

[name], MPH (See Appendix C for CV)

1.3.c. Sub-Investigator

[figure not shown]
[name] (See Appendix D for CV)

1.3.d. Form FDA 3454

See Appendix E

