We will use generalized estimating equations (GEE) to estimate treatment effects on repeated study outcomes. Primary analyses will be by intention-to-treat, without regard to adherence to treatment. In our prior trials, we had excellent retention and visit adherence. Nonetheless, in this high risk population, missing data may be encountered.^{175,176} We will conduct sensitivity analyses imputing all missing urine samples as positive, adjusting for baseline correlates of missingness, and using inverse probability of censoring weights.¹⁷⁷

Aim 1: To determine the efficacy of targeted kudzu versus placebo in reducing binge drinking among sexually active binge drinkers with AUD, as determined by number of binge drinking days in timeline follow-back (TLFB), by treatment arm. GEE Poisson models with robust standard

errors will be used to assess reductions on weekly drinking outcomes. Baseline TLFB results will be included in the analysis. Minimum detectable effects (MDEs): Based on the prior Project iN trial (93% retention), we conservatively estimate that 80% of participants will be retained at 12 weeks. Using estimates based on Project ECHO for the within-subject correlation and over-dispersion of the outcomes, as well as the mean frequency among controls, we estimate that this study will have 80% power in 2-sided tests with a type-I error rate of 5% to detect 28% reductions in numbers of binge drinking occasions, as well as 11% reductions in the average number of drinks on drinking days. In exploratory analyses, we will evaluate the durability of intervention effects on drinking outcomes at 1- and 3-month post-treatment visits.

Aim 2: *To determine the efficacy of targeted kudzu versus placebo in reducing alcohol consumption among non-dependent individuals with AUD*, as determined by the proportion of ethyl glucuronide (EtG) positive urines, by treatment arm. GEE logistic models with robust standard errors will be used to assess reductions frequency of positive urine tests, accounting for within-subject correlation. MDEs: Using the assumptions for retention for Aim 1, as well as estimates based on biomarker data from [name] et al.'s study on topiramate for alcohol use disorders¹⁷⁴ for the within-subject correlation and control group urine positivity rate, we estimate that the study will have 80% power in 2-sided tests with a type-I error rate of 5% to detect 15-24% reductions in the urine positivity rate in the treatment arm.

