Aim 3: *To determine the efficacy of targeted kudzu versus placebo in reducing alcohol-associated sexual risk behaviors and incidence of STIs*, by treatment arm, we will use GEE Poisson models with robust standard errors for the four monthly ACASI assessments on numbers of sex partners, HIV-serodiscordant condomless sex partners, condomless sex partners while intoxicated with alcohol, and condomless sex events with serodiscordant partners, including the baseline value. In the event that these outcomes are severely over-dispersed, we will analyze indicators for any self-report of each behavior, using GEE logistic models. We will use GEE logistic regression models to evaluate differences in incidence of STIs between kudzu and placebo arms over time. Incidence will be evaluated as a composite outcome (i.e., any incident STIs), as well as by type (i.e., incident syphilis, gonorrhea, or Chlamydia), and, for gonorrhea and Chlamydia, by site (i.e., urethral, oral, vaginal, or rectal). MDEs: Based on estimates of within-subject correlation and control prevalence from our Project Echo trial, we estimate that the study will have 80% power to detect 32% reductions in numbers of male anal sex partners, 59% reductions in serodiscordant condomless anal sex partners, 48% reductions in condomless anal sex partners while intoxicated with alcohol, and 58% reductions in condomless anal sex events with serodiscordant partners in the treatment arm. In analyses using GEE logistic models, we will have 80% power to detect reductions of 15% for any male anal sex partners, 39% for any HIV-serodiscordant condomless anal sex partners, 40% for any condomless anal sex partners while intoxicated with alcohol, and 31% for any condomless anal sex events with serodiscordant partners in the treatment arm. After accounting for expected loss to follow-up, we will have an estimated 80% power in 2-sided tests with a type-I error rate of 5% to detect reductions of 23-26 percentage points in the incidence of STIs at month 3, depending on the control rates, assumed to be in the range 30-40%, and within-subject correlation of these outcomes, assumed to be 0.1 to 0.3; both inputs were based on data in an ongoing PrEP demonstration project.

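### Four unranked primary objectives and seven or eight efficacy tests, with no primary endpoint or multiplicity control: about a 25–34% chance of some false positive, 13–18% of one favouring kudzu

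*Combined protocol and SAP*

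**What the plan says.** Section 1.2 introduces all four aims with "The primary objectives of this study are as follows". Aims 1 to 3 are to determine efficacy: on binge drinking, on EtG-positive urines, and on sexual risk behaviour and STI incidence. Aim 4 is tolerability and acceptability. No aim is placed above another.

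Section 1.7 sets out the tests:

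- **Aim 1.** The power statement claims "80% power in 2-sided tests with a type-I error rate of 5% to detect 28% reductions in numbers of binge drinking occasions". It adds an 11% reduction in drinks on drinking days, an outcome that is in sections 1.4 and 1.7 but not in the section 1.2 aim.
- **Aim 2.** "GEE logistic models with robust standard errors will be used to assess reductions frequency of positive urine tests". Its power statement also uses a two-sided 5% rate.
- **Aim 3, behaviour.** There are four count outcomes. The power statement, "we estimate that the study will have 80% power to detect 32% reductions in numbers of male anal sex partners" and so on through the four, gives no significance level. If the counts are severely over-dispersed, the models switch to logistic; no threshold is set.
- **Aim 3, STIs.** "Incidence will be evaluated as a composite outcome (i.e., any incident STIs), as well as by type", and by body site for gonorrhoea and chlamydia. The power statement uses a two-sided 5% rate.
- **Aim 4.** Adverse events and adherence only, with no efficacy test.

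Section 1.7 names intention-to-treat as the primary analysis approach, but it names no primary endpoint, hierarchy, alpha split or multiplicity adjustment. The section on trial stopping rules excludes a formal interim efficacy analysis, so repeated looks add no error.

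**The concern.** With several efficacy outcomes of equal standing and no rule linking them to a conclusion, a significant result on any one outcome under Aims 1 to 3 could be presented as meeting a primary objective. A reader of the results could not tell a planned success from a selected one.

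The plan's own logic also needs a primary endpoint. Section 1.7 calls for a marginal structural model sensitivity analysis when the evidence for efficacy is weak but falls short of significance. With seven or eight unranked tests, that condition has no defined meaning.

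**Working it through.** **1. The plan's own figure.** The stated rate is a two-sided 5% per test. One test gives a 5% chance of a false positive in either direction, and 2.5% in favour of kudzu. No familywise figure is stated, so there is none to reproduce.

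**2. Count of tests (sections 1.2 and 1.7).**

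| Source | Tests |
|---|---|
| Aim 1, binge drinking | 1 |
| Aim 2, EtG positivity | 1 |
| Aim 3, sexual behaviour | 4 |
| Aim 3, any incident STI | 1 |
| **Total by section 1.2** | **7** |
| Drinks on drinking days (1.4 and 1.7 only) | 1 |
| **Total by section 1.7** | **8** |
| STI by type | 3 |
| STI by site (2 organisms × 4 sites) | up to 8 |

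The 5% is explicit for four of the eight (both Aim 1 outcomes, EtG and the STI composite) and assumed for the four behaviour outcomes.

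**3. Independent tests.**

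- Eight, either direction: 1 − 0.95^8 = 33.7%.
- Eight, favouring kudzu: 1 − 0.975^8 = 18.3%.
- Seven, either direction: 1 − 0.95^7 = 30.2%.
- All 19 with STI breakdowns: 1 − 0.95^19 = 62.3% in either direction; 1 − 0.975^19 = 38.2% favouring kudzu.

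**4. Correlated tests.** The documents give no between-endpoint correlation, so ρ is an assumption. For k equicorrelated normal statistics with c = 1.96,

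P(at least one) = 1 − ∫ [Φ((c − √ρ·u)/√(1 − ρ)) − Φ((−c − √ρ·u)/√(1 − ρ))]^k φ(u) du.

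The second Φ is dropped to count only results favouring kudzu.

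| ρ | 8 tests, either direction | 8 tests, favouring kudzu | 7 tests, either direction |
|---|---|---|---|
| 0 | 33.7% | 18.3% | 30.2% |
| 0.3 | 30.0% | 15.2% | 27.1% |
| 0.5 | 25.0% | 12.5% | 23.0% |
| 0.7 | 19.1% | 9.5% | 17.8% |
| 0.8 | 15.7% | 7.9% | 14.9% |

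A simulation with three drinking outcomes, four behaviour outcomes and one STI outcome in blocks (correlation 0.3–0.7 within the drinking and behaviour blocks, 0.1–0.2 elsewhere) gave 26–32% in either direction and 13–17% favouring kudzu.

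**5. Effect of each remedy.** One designated primary test returns the rate to 5% and leaves the 28% detectable effect alone. Bonferroni over eight uses 0.05/8 = 0.00625 per test. The familywise rate is then 4.9% if the tests are independent, and at most 5% under any correlation. The inputs behind the 28% (control mean, over-dispersion, within-subject correlation) are not given, so it can only be rescaled on the log rate-ratio scale:

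1 − exp[ln(0.72) × (2.734 + 0.842)/(1.960 + 0.842)] = 1 − exp(−0.3285 × 1.276) = 34%.

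Adjusting all eight would therefore raise the detectable reduction in binge occasions from 28% to about 34%.

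**The case against.** **The trial is called a pilot.** That softens the consequence but does not remove the problem. Section 1.4 calls it an efficacy study, section 1.5.f states the aim as determining efficacy in reducing binge drinking, and Aims 1 to 3 carry formal power statements. The plan keeps the word exploratory for other analyses, such as post-treatment durability.

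**Each aim can be judged alone.** Section 1.2 ties Aim 1 to one measure and Aim 2 to one measure, so a claim confined to either keeps its own 5%. That is fair as far as it goes. Two such tests give 1 − 0.95^2 = 9.8% if independent. Aim 3 alone has five, giving 1 − 0.95^5 = 22.6%, and nothing in the plan confines the efficacy conclusion to one aim.

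**A reader might infer more than the documents support.**

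- The 25–34% is not the chance of a false claim that kudzu works. It includes false results against kudzu; the figure in its favour is about half.
- The plan does not misstate a 5% overall error rate. It gives 5% per test and no overall rate.
- The efficacy tests do not come from all four objectives. Aim 4 has none.

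**The correlations are assumed.** This stands. Several behaviour outcomes overlap, and stronger correlation lowers the figures, but even at 0.8 the either-direction rate is about three times 5%.

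**The choice of endpoint belongs to the sponsor.** Also true: any hierarchy fixed in advance would close the gap. Binge drinking is suggested because it is Aim 1's measure and the purpose stated in section 1.5.f.

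**Conclusion.** The point holds. Seven efficacy tests under section 1.2, or eight under section 1.7, have no primary endpoint, order or error control. If all eight are run at two-sided 5%, the chance of at least one false positive in either direction is about 25–34% (correlation 0.5 to 0; 19% at 0.7). For seven tests it is about 23–30%. The chance of a false result favouring kudzu with eight tests is about 13–18%, five to seven times the 2.5% for one test. These figures rest on the assumed correlations and on carrying the 5% over to the behaviour outcomes. STI breakdowns by type and site would add to them.

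No planned analysis is invalid in itself. What is undefined is which result decides efficacy. This should be corrected, and it can be done without new data or participants.

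**What to change.** Amend sections 1.2 and 1.7 before unblinding:

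1. Name the timeline follow-back binge-drinking outcome over the 12 weeks as the single primary endpoint, at two-sided 5%.
2. Use one term for it. Section 1.2 says days, section 1.4 and the power sentence in 1.7 say occasions, and Table 3 says sessions. The 28% detectable effect is stated for occasions, so if days is chosen, confirm that the figure applies.
3. Make EtG positivity, then drinks per drinking day, key secondary endpoints tested in that fixed order.
4. Make the Aim 3 outcomes secondary with Holm adjustment, or label them hypothesis-generating.
5. Leave the Aim 4 analyses as planned; they add nothing to the efficacy error.

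The sample size of 120 and the 28% detectable effect do not change. The cost is a protocol amendment with IRB approval and notice to the NIH program officer and the DSMB, as the section on reporting of other study events requires. Section 1.4.g shows that participants were already in the trial, so the amendment should record that the ranking was fixed while the treatment code was closed. The other cost is that a positive result on a lower-ranked outcome alone can no longer be called a primary result.

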1.4 Study Design

This study is a double-blind, placebo-controlled, two-arm trial in which 120 binge drinkers with AUD will be randomly assigned to receive 12 weeks of kudzu or placebo, to be taken on an as-needed basis (see Figure 2) with 1- and 3-month post-treatment follow-up visits. This efficacy study will enroll sexually active, binge drinkers with AUD because they are the most likely population to benefit from this intervention by limiting harms associated with heavy alcohol use and decreasing alcohol-related sexual risk behaviors. A study clinician will perform the Structured Clinical Interview for the DSM-V (SCID) to screen for AUD and determine eligibility. Upon enrollment, 120 participants will be randomized 1:1 to kudzu extract (2 grams) or placebo for targeted administration. Participants will be seen weekly for behavioral surveys, urinalyses, study drug dispensing, and alcohol use counseling. Safety laboratory assessment, vital signs, and the audio computer assisted survey instrument (ACASI) will be completed monthly. Efficacy, tolerability, and acceptability (Specific Aims 1-4) will be assessed upon trial completion as measured by number of binge drinking occasions and numbers of drinks on drinking days via timeline follow-back at weekly visits; number of EtG-positive urine samples; sexual risk behavior data through monthly surveys via ACASI; frequency of adverse events; and cumulative medication adherence data at week 12. Durability of intervention effects will be evaluated at 1- and 3-month post-treatment visits.

1.4.a. Study Participants, recruitment, and inclusion/exclusion criteria. We will recruit a total of 120 racially/ethnically diverse sexually active, binge drinkers with AUD will be enrolled in the study. Subjects will be San Francisco Bay Area residents between 18-70 years of age. The project is designed specifically for binge-drinkers at high risk for HIV transmission or acquisition.

1.4.b. Recruitment.

For this study, we will combine several strategies that have proven successful in our previous studies with alcohol- and substance-using individuals:

Advertisements: We will run advertisements in the local papers catering to the community and widely read by our participants.

Internet recruitment: As in our current studies, Internet-based recruitment will occur through strategic placement of banner ads on Web sites frequented by alcohol-using individuals, including craigslist.org, Facebook, manhunt.net, Adam4Adam.com, BarebackRt.com and tweaker.org, and on smart phone mobile applications for this population, including Grindr, Instagram, Manhunt Mobile, and BarebackRt Mobile. Additionally, we will use targeted ads for San Francisco Bay Area on Facebook and Google Adwords.

Active recruitment: We will recruit on the street in neighborhoods and at fairs frequented by alcohol-using individuals, collecting phone numbers of interested potential participants, and leaving cards and fliers in LGBT meeting places, local community-based organizations (CBOs), bars, and clubs. We will also recruit at clinics with many alcohol-using patients such as the Health Department's STD clinic (City Clinic) and the public HIV clinic at San Francisco General Hospital (SFGH).

Snowball sampling: Study participants are encouraged to refer their friends by taking cards and fliers so that potential participants can call us. This is a method to reach some people we may miss via our other recruitment strategies.

In addition, we will also recruit participants that screen ineligible for our other ongoing NIH-funded studies. Prospective and former participants from our ongoing trials will be asked if they are willing to be contacted for future studies; participants who provide consent will have their contact information saved in a database for future contact. Once this study is running, potential participants will be triaged with a pre-screening process that directs them to the study for which they are most likely to be eligible, an approach we have found to be effective and efficient for our parallel methamphetamine trials.

1.4.c. Retention.

We have a proven record of high retention rates in our studies, including among alcohol-using MSM. We anticipate an 80% retention rate over the 12 weeks of follow-up for this study. While we realize that retention among substance users is considerably challenging, we believe our goal is realistic and feasible. We acknowledge, however, that extra efforts will be needed to ensure

that our study participants adhere to the study protocol, and we will make every effort to meet and hopefully exceed our retention target.

First, study staff will be trained to be alert for any factors that signal a low likelihood of the participant being able to adhere to the study schedule; for example, participants who are unable to provide contact information or who miss or re-schedule screening visits are retention risks. Whether or not to enroll such persons will be determined on a case-by-case basis.

We will use a variety of up-front and long-term strategies from our prior studies to achieve excellent retention rates. At screening, participants will be asked to provide extensive locating information, including home addresses, cell and home phone numbers, and e-mail addresses for themselves, and to provide the names of two local persons to be contacted in the event that the participant cannot be reached. We will attempt to contact persons on this list only in the event that multiple attempts to reach the study participant directly fail; at no time will we divulge information about the study or the participant to these contacts. Contact information will be updated every four weeks, or more frequently as necessary. We have found these procedures to be highly acceptable to participants.

We have also found that scheduling out appointments in advance is useful for helping participants to understand the frequency of visits and for maintaining higher retention rates. This is easily done using our Wellsky® appointment scheduling software. Each participant is also provided with a wallet-sized appointment card containing study staff contact information. Future appointments are reviewed and rescheduled as needed. For missed or canceled visits, we contact participants by their selected form of communication (home telephone, cell phone, e-mail, text message, etc.) within 24 hours to reschedule by making up to three attempts to contact individuals at different times of day. We will also attempt to reach up to two alternate contacts provided by the participant at enrollment.

1.4.d. Inclusion Criteria.

Subjects must meet *all* of the following inclusion criteria to be eligible for participation in this study:

1. Self-reported anal or vaginal sex in the prior three months while under the influence of alcohol, or reported missing ART or PrEP due to alcohol use in the prior 3 months; ;
2. At least one binge-drinking (five or more drinks on a single occasion for men; four or more drinks for women) session per week in the prior three months;
3. Having an AUD by DSM-5 SCID criteria (includes hazardous and harmful use);
4. Interested in reducing binge alcohol consumption;
5. HIV negative by rapid antibody test or HIV positive with a medical record documentation of HIV infection*. For HIV-positive individuals, having a CD4 cell count >100 cells/mm³ and having suppressed HIV viral load with < 50 copies/mm³;
6. No current acute illnesses requiring prolonged medical care;
7. No chronic illnesses that are likely to progress clinically during trial participation;
8. Able and willing to provide informed consent and adhere to visit schedule;

9. Age 18-70 years;
10. Baseline CBC, total protein, albumin, glucose, alkaline phosphatase, creatinine, BUN, and electrolytes without clinically significant abnormalities as determined by study clinician in conjunction with symptoms, physical exam, and medical history.

***Note:** Participants newly diagnosed with HIV at screening are eligible for the study but we will postpone their enrollment until they are virally suppressed with HIV viral load < 50 copies/mm³.

1.4.e. Exclusion Criteria.

Subjects who meet *any* of the following exclusion criteria are not to be enrolled in this study:

1. Any psychiatric (e.g., depression with suicidal ideation) or medical condition that would preclude safe participation in the study;
2. Known allergy/previous adverse reaction to kudzu;
3. Moderate/severe liver disease (AST, ALT \geq 5 times upper limit of normal);
4. Impaired renal function (creatinine clearance < 50 ml/min);
5. Currently participating in another intervention research study with potential overlap;
6. Current severe substance use disorder (exclusive nicotine, cannabis and alcohol) as determined by DSM-V SCID criteria;
7. pregnant women;
8. HIV positive individuals who are not virally suppressed;
9. Any condition that, in the principal investigator and/or study clinician's judgment interferes with safe study participation or adherence to study procedures;
10. Not willing to learn how to send EMA surveys

*Eligible participants who have a partner currently in the study will be enrolled and randomized after their partner has completed their in-treatment follow-up, to reduce the concerns of contamination between treatment conditions.

1.4.f. Community input on recruitment and retention.

Center for Public Health Research's (CPHR) Community Consulting Group (CCG) is a panel of HIV treatment advocates, community stakeholders, and diverse staff from a range of community-based organizations that meets quarterly to share input about current and future research endeavors within the CPHR. The CCG includes health care providers, substance abuse experts, and other individuals familiar with the unique needs of substance-using individuals, and has a long history of partnership with the San Francisco Department of Public Health (SFDPH). This sustained association has afforded valuable opportunities for the community to provide substantial and pertinent input concerning our research and has been invaluable in helping to develop culturally competent intervention content and effective recruitment and retention strategies.

1.4.g Study Procedures.

Potential participants will be asked brief eligibility screening questions in person or over the phone after providing verbal consent. Potential participants will provide informed consent and be screened for eligibility during the pre-enrollment screening visit. The schedule for the study

procedures is shown in (see Figure 2). Participants will be compensated for their time at each visit (up to a total of \$444). Participants will receive \$50 for the 2 screening visits (\$25 each visit), \$50 for enrollment, \$10 for weekly visits (1, 2, 3, 5, 7, 9, 10, and 11), \$25 for weeks 4 (month 1) and 8 (month 2) visits, \$30 week 6 safety lab visit and \$50 for week 12. In addition, they will receive \$1 for each day that they complete the text-messaging series throughout the 12-week treatment period (up to \$84). Consistent with other trials, we will conduct 1- and 3-month post-treatment visits to evaluate durability of treatment.¹³⁹⁻¹⁴² For post-treatment visits, participants will receive \$25 (see Figure 2).

We are currently implementing the Interim UCSF Policy on Human Subjects-Related Research visits during the COVID-19 outbreak. The A-Hack study is considered essential research. We have stopped screening and enrollment visits until the shelter-in-place order is lifted. The weekly and post-treatment visits are being conducted remotely according to the interim policy guidelines. We have given the active participants up to 6 weeks of study medication during the shelter-in-place order. The monthly visits (M1, M2 and M3) include safety labs to ensure that participants do not have any adverse events to study medication. We are proposing that these in-clinic visits are conducted at weeks 6 and 12 instead of monthly for the safety of our participants during the shelter-in-place order. We will evaluate the interim policy each two weeks or when necessary according to UCSF IRB guidelines.

1.5.a. Prescreening.

Potential participants will be asked brief eligibility screening questions in person or over the phone after providing verbal consent.

1.5.b. Consent.

The consent process will discuss the 1:1 random assignment of participants to receive kudzu or placebo and will detail the potential adverse effects of kudzu. It will also discuss the weekly substance use counseling sessions. The consent process also addresses participant rights, including the voluntary nature of participation and ability to decline without penalty. Mechanisms for maintaining confidentiality will also be discussed, as well as exceptions to confidentiality which is required by law. Participants will be given a copy of the Human Subject's Bill of Rights, along with a copy of the consent form. Participants are given the contact numbers of both the PI and the UCSF IRB to answer questions about the study or one's rights as a human subject. All participants will meet with a study clinician for an additional opportunity to ask questions. Similar to our prior pharmacologic studies, all participants must also correctly complete an "Assessment of Understanding" quiz. The quiz will include 10 to 12 true/false study-related questions that assess participants' understanding of basic study concepts, including the unknown efficacy of kudzu to reduce heavy alcohol use, its side effect profile, the randomization process, and the nature of placebos. After the assessment of understanding has been completed and staff are satisfied that the participant is able to give full informed consent (including, but not limited to, a participant completing the quiz with an 80% score or greater and a demonstrated ability to fully understand corrected answers), the consent form will be signed by the participant. The staff member obtaining consent will also sign both the original

and the copy as a witness, completing the informed consent process. A copy of the signed form will be given to the client; the original signed consent will be kept in a separate, locked file.

1.5.c. Screening.

Potential participants will be screened using the inclusion and exclusion criteria outlined above in sections I.2.d & I.2.e. The screening process will consist of two visits.

1.5.d. Randomization.

Participants will be randomly assigned, sequentially as they qualify for the study, to either kudzu or placebo in a 1:1 ratio per a computer-generated list, stratified by gender, provided by a biostatistician. Randomization will be balanced using permuted blocks. Stratification by gender will ensure balance of treatment assignment within genders. Participants and investigators will be blinded to assignment.

1.5.e. Procedures for assignment to a study group, and medication dispensing.

Participants will be assigned to kudzu or placebo by a double-blinded block randomization procedure, stratified by gender. The stratified randomization code, which will have variable blocks and 1:1 randomization, will be provided by the statistician directly to the pharmacy. No study staff will have access to the code. Study medication (kudzu and placebo) will be prepared by pharmacists at Natural Pharmacie International (NPI) in identical, absorbable gelatin caps to maintain the double-blind. The study drug will be dispensed by the study clinicians in MEMs cap dispensers with dosing instructions, date of dispensing, prescribing clinician, a 24-hour telephone study phone number for medical emergencies, and advisements against drug combinations. Participants will be trained on targeted dosing of medication during enrollment and be provided a quick guide instructional leaflet for reference. Consistent with prior targeted dosing studies, participants will be instructed to take a single 2 gram dose when they believe that drinking is imminent or anticipate a drinking session.⁵⁶ For the proposed study, a single dose of the study drug will be comprised of four 500 mg capsules of kudzu extract (NPI-031, Natural Pharmacia International, Belmont, MA) or matching placebo, which is consistent with a recent human laboratory study that established the quick-acting, protective effect of a single dose of kudzu.⁸⁸ Participants will be given seven 2 gram doses (28 500 mg capsules) per week and will be instructed to not exceed a single dose (4 capsules) every 24 hours.⁵⁶ Participants will be briefed about the importance of not sharing medications.

1.5.f. Medical Management.

This study's aim is to determine efficacy of an herbal intervention to reduce binge drinking, against a background of relatively brief counseling that would be feasible in a clinical setting with limited resources. Thus, we will adapt a manualized version of the MM brief counseling platform used in NIAAA's COMBINE study.^{150,151} In that trial, pharmacotherapy with MM showed the most significant reductions in heavy drinking days compared to 7 other treatment arms.¹⁵⁰ MM has been used in a targeted pharmacotherapy trial 98 and our team has

successfully used MM in AUD trials. MM is a low-intensity supportive program designed to increase problem recognition and enhance motivation to change maladaptive alcohol use patterns. Participants will receive individual 20 minute MM sessions weekly from trained staff supervised by a clinical psychologist.

1.1. Measures and Schedule of Data Collection Overview.

1.1.a. Medical Safety Measures.

Blood specimens will be collected for monthly safety lab assessments via venipuncture by clinicians or research associates with certified phlebotomy training. Since San Francisco is facing the COVID-19 outbreak, we will collect safety lab assessments at 6 and 12 weeks* rather than monthly until the shelter-in-place order is lifted. This is for the safety of our participants.

Table 3: Summary of Measures	Data Source	Schedule*
OUTCOME VARIABLES		
Alcohol behavioral outcomes ^{152,153}		
No. of binge drinking sessions; drinks per drinking day	TLFB ¹⁵⁴ ; SMS texts	W, D, PT
Alcohol urinary biomarker		
Urine-positivity for ethyl glucuronide (EtG) for recent alcohol use (past 3 days)	Urine Sample	E, W-6, PT
Sexually Transmitted Infections outcomes		
Incident syphilis, gonorrhea, Chlamydia, or HIV; site of infections (urethral, oral or rectal).	Biologic Samples	E, M-3, PT
Behavioral outcomes ^{152,153}		
No. of sex partners and condomless sex acts; Event-level data on alcohol and recent episodes of sex ¹⁵⁵ ; Partners on PrEP or with undetectable viral load	ACASI, S MS texts	E, M, D, PT
PrEP use and adherence / Anti-retroviral Therapy (ART) use and adherence	ACASI	E, M
Reported days / episodes of other substance use	ACASI	E, M
Alcohol treatment (outside study)	ACASI	E, M
Adherence outcomes		
Frequency and timing of pill taking	MEMs cap Dispensers	D
Self-reported adherence	ACASI; SMS texts	M; D
Safety outcomes		
Adverse events ¹⁵⁶	Self-report	E, M
Safety labs (e.g., liver enzyme levels, renal function) ¹⁵⁶	Serum Sample	E, M*
Surrogate measures for hypothesized kudzu mechanisms		
Alcohol physiological effects, mood states and risk behaviors during drinking sessions ¹⁵⁷	ACASI	W
Alcohol subjective effects scale (SES) on intensity of intoxication and of impairment ; Length of subjective effects of first alcohol drink; ¹⁵⁸ Desire for alcohol ¹⁶⁸	ACASI	W
Binge-drinking score from Alcohol Use Questionnaire; ^{159,160} Speed of drinking/drinking rate; ¹⁶¹ Latency/time delay between first and second drink during drinking sessions ¹⁶¹	ACASI	W
Biphasic alcohol effects scale (BAES) for subjective nature of intoxication (stimulation and sedation) ¹⁶²	ACASI	W
Trial process measures		
No. pre-screened, screened, enrolled; visits attended, overall retention; participant satisfaction with trial	Visit database, ACASI	Ongoing M 3
Additional covariates		
Demographics (e.g., age, race, education)	ACASI	E
Alcohol Use Disorders Identification Test (AUDIT) ¹⁶³	ACASI	E, M
Center for Epidemiologic Studies Depression Scale ¹⁶⁴	ACASI	E, M
Brief Symptom Inventory ¹⁶⁵	ACASI	E, M
Severity of Dependence Scale ¹⁶⁶	ACASI	E, M
Visual Analog Scale Craving Scores ¹⁶⁷	ACASI	E, W

Notes: E=Enrollment; M=Monthly; W=Weekly; D=Daily PT=Post-Treatment

than monthly until the shelter-in-place order is lifted. This is for the safety of our participants.

Medications taken 30 days prior to enrollment and while enrolled in the study will be documented on a concomitant medications form.

1.1.b. Potential Risks.

Adverse drug effects: A primary risk of participation in this study is the potential of AEs due to taking kudzu. As part of the informed consent process, participants will be informed of the potential risks of taking kudzu. As an edible plant, the roots, flowers and leaves of kudzu has long been used for a wide range of food recipes and consumed as tea in East Asia.⁶³ Hence, kudzu is believed to be extremely safe for human consumption.

